7.2 NULL AND ALTERNATIVE HYPOTHESES

No formal hypothesis testing is planned in this trial. All analyses in this trial are descriptive and exploratory.

In cohort F, statistical criteria are defined and will be evaluated at the end of stage II. Please refer to [Section 7.1.2](#) for more details on the final criterion and analysis.

7.3 PLANNED ANALYSES

No per protocol set will be used in the analysis. However, important protocol deviations will be summarized. The TSAP will specify the important protocol deviations in detail.

For the determination of the MTD, only MTD-evaluable patients will be considered. For the analysis of secondary and [REDACTED] in Part 1, all patients in the treated set (i.e., patients treated with at least one dose of trial medication) will be included in the analysis. All analyses planned in Part 2 will be based on the treated set.

7.3.1 Primary endpoint analyses

7.3.1.1 Primary endpoint analyses for Part 1

In order to identify the MTD(s) and the recommended dose(s) for Part 2 of the trial, the number of patients with DLTs at each dose combination during the Part 1 MTD evaluation period (the first cycle of the BI 836880 plus ezabenlimab combination) must be presented by descriptive statistics. Patients who discontinue during the first treatment cycle for reasons other than a DLT will be excluded from the determination of the MTD. In addition, the number of patients with DLTs that occurred during the entire treatment period will be summarized at each dose level. The BLRM will be rerun to re-evaluate the MTD and RP2D together with all relevant data collected during Part 2.

7.3.1.2 Primary endpoint analyses for Part 2

The primary endpoint for Part 2 of the trial is OR defined by confirmed CR or PR according to RECIST 1.1 for all cohorts except GBM as assessed by the Investigator. OR in GBM cohort will be evaluated using RANO criteria. Overall response will be analyzed in terms of the shrinkage estimator of the OR rate (ORR) based on BHM.

Note on primary endpoint analysis in cohort F:

In addition, OR from stage I and stage II will be analyzed separately using a Bayesian approach with meta-analytic predictive (MAP) prior after completion of stage II. Please refer to [Section 7.1.2](#) for more details on the derivation of the MAP prior and the final decision criterion. A naïve estimate (observed objective response rate) along with 95% CI (Clopper-Pearson) will also be provided.

7.3.2 Secondary endpoint

7.3.2.1 Secondary endpoint analyses for Part 1

All Adverse Events (AEs), drug related AEs and drug related AEs leading to dose reduction or discontinuation during treatment period will be summarized descriptively.

Details on statistical inference for PK parameters, e.g., Cmax , tmax, AUC0-504h, and accumulation ratios RA after the first (Part 1 and 2) and fourth (Part 1) infusion cycle are described in [Section 7.3.5](#).

7.3.2.2 Secondary endpoint analyses for Part 2

Disease control (DC) will be analyzed in terms of DC rate (DCR), defined as the proportion of patients with best overall response of CR, PR, or SD according to RANO for GBM & RECIST1.1 for all other cohorts. Proportions will be presented with 95% two-sided confidence interval using the exact Clopper-Pearson method.

Duration of objective response (DoR) - for all patients with an OR, the duration of OR is defined as time from first documented CR or PR to the earliest of disease progression or death among patients with OR. If a patient did not die or progress until the last visit in the study, this patient will be censored at the last time point known to be alive and progression-free. The outcome will be assessed according to RANO for GBM & RECIST 1.1 for all other cohorts.

[figure not shown]
Progression-free survival (PFS) is defined as time from first treatment infusion until disease progression or death from any cause, whichever occurs earlier. If a patient did not die or progress until the last visit in the study, this patient will be censored at the last time point known to be alive and progression-free.

Kaplan-Meier estimates will be used to analyze duration of OR and PFS.

Tumor shrinkage, the difference between the minimum post-baseline sum of lesion of target lesions and baseline sum of the same target lesions, will be summarized descriptively.

PK parameters analyses for Cmax, tmax, AUC0-tz, CL, t1/2, and Vss after the first and fourth infusion cycle will be detailed in the TSAP.

7.3.4 Safety analyses

Adverse events will be coded using the Medical Dictionary for Drug Regulatory Activities (MedDRA). Standard BI summary tables and listings will be produced. All adverse events with an onset between start of treatment and end of the residual effect period (REP), a period of 42 days after the last dose of trial medication and adverse event that start before first dose of trial medication but deteriorate during treatment, will be considered “treatment-emergent” and be assigned to the on-treatment period for evaluation.

[figure not shown]
All treated patients will be included in the safety analysis. In general, safety analyses will be descriptive in nature and will be based on BI standards. No hypothesis testing is planned.

Statistical analysis and reporting of adverse events will concentrate on treatment-emergent adverse events, i.e. all adverse events occurring between start of treatment and end of the residual effect period. Adverse events that start before first drug intake and deteriorate under treatment will also be considered as ‘treatment-emergent’.

Frequency, severity, and causal relationship of adverse events will be tabulated by system organ class and preferred term after coding according to the current version of the Medical Dictionary for Drug Regulatory Activities (MedDRA).

Laboratory data will be analyzed both quantitatively as well as qualitatively. The latter will be done via comparison of laboratory data to their reference ranges. Values outside the reference range as well as values defined as clinically relevant will be summarised. Treatment groups will be compared descriptively with regard to distribution parameters as well as with regard to frequency and percentage of patients with abnormal values or clinically relevant abnormal values.

Vital signs, physical examinations, or other safety-relevant data observed at screening, baseline, during the course of the trial and at the end-of-trial evaluation will be assessed with regard to possible changes compared to findings before start of treatment.

7.4 INTERIM ANALYSES

Part 1:

Interim safety evaluations will be performed as considered necessary. The dose-escalation design dictates that the sponsor and the SMC perform regular safety evaluations. Safety evaluations will be performed after each dose cohort by the SMC. The SMC will recommend the next dose level as well as the corresponding cohort size. SMC will recommend the RP2D that will be used in Part 2. SMC meeting minutes and outputs provided for these SMC meetings will be documented and archived.

Exploratory analyses of PK/PD may be performed at the end of Part 1 and additionally if considered informative for the study.

Part 2:

In Part 2, 290 patients are planned to be treated. 40 patients each are planned for cohorts A and B, and 30 patients each are planned for cohorts C, D, E, G, and H. In addition, as of protocol version 7, 30 more patients will be enrolled in addition to previously enrolled 30 patients in cohort F. The Sponsor may pause enrollment in any cohort at any time to carefully evaluate the safety and efficacy data of patients already enrolled in a given cohort.

An interim futility analysis will be performed for cohorts C, D, E, F, G, and H in Part 2. The interim analyses for each cohort are planned to be conducted after 15 patients in that cohort have completed their two on-treatment imaging assessments (i.e., end of cycle 4 or later depending on the cohort). For each cohort, timing of the interim analysis may be adjusted according to actual recruitment rate to facilitate or avoid delay of the trial conduct. The Sponsor may pause enrollment in a cohort before making any decisions from the interim futility analysis. The two-stage design is planned to stop further recruitment of patients if the defined efficacy boundary (see [Table 7.7.2: 1](#)) is not met at the first stage.

Exploratory analyses of PK/PD may be additionally performed during Part 2 and if considered informative for the study.

7.5 HANDLING OF MISSING DATA

information on all AEs, with particular emphasis on potential DLTs. For partial or missing AE onset and/or end dates, BI internal rules will be followed (see Reference Document 001-MCG-156_RD01 “Handling of missing and incomplete AE dates”).

7.6 RANDOMIZATION

No randomization will be performed. In Part 1, patients will be assigned to escalating dose groups by order of admission into the trial.

7.7 DETERMINATION OF SAMPLE SIZE

7.7.1 Determination of sample size for Part 1

For Part 1, no formal statistical power calculations of sample size were performed. Approximately 12-18 patients will be expected for the dose finding part and confirmation of RP2D. Fewer patients might be needed based on the recommendation of the SMC and the actual number of cohorts tested.

7.7.2 Determination of sample size for Part 2

For Part 2, below cohorts assume:

- Cohort A:
 - patients with locally advanced or metastatic non-squamous Non-Small Cell Lung Cancer with CPI monotherapy.
- Cohort B:
 - patients with locally advanced or metastatic non-squamous Non-Small Cell Lung Cancer pre-treated with a combination of platinum-based chemotherapy and checkpoint inhibitor.
- Cohort C:
 - patients with locally advanced or metastatic Small Cell Lung Cancer, with no more than one line of chemotherapy, except platinum sensitive patients.
- Cohort D:
 - patients with histologically confirmed recurrent glioblastoma (primary), **No more than two lines of prior chemotherapy** (concurrent and adjuvant temozolomide based chemotherapy including in combination with another investigational agent is considered one line of chemotherapy).
- Cohort E:
 - patients with histologically confirmed, unresectable, Stage IV metastatic melanoma, with least one line of any kind of immune therapy.
- Cohort F (2nd line HCC):
 - patients with locally advanced or metastatic and/or unresectable Hepatocellular Carcinoma who were intolerant or progressed during 1st line sorafenib or lenvatinib treatment.

- Cohort G (1st line HCC):
 - patients with locally advanced or metastatic and/or unresectable HCC with no prior systemic treatment.
- Cohort H (2nd line HCC – atezolizumab+bevacizumab failure only):
 - patients with locally advanced or metastatic and/or unresectable HCC who were intolerant or progressed during 1st line atezolizumab+bevacizumab treatment.

A total of approximately 290 patients will be treated for these 8 cohorts. 40 patients each are planned for cohorts A and B, and 30 patients are planned for cohorts C, D, E, G, H and 60 patients for cohorts F.

For cohorts A, B, E, and H, there is no literature available for the target patients. As there are no treatments of proven efficacy for this population, it is assumed around 5% ORR with background therapy. The futility boundary for cohort E and cohort H is set as 7% at planned interim futility analysis timing. The early stopping probabilities are shown in [Table 7.7.2: 1](#).

For cohort C (SCLC), around 20% ORR with anti-PD-1 antibody monotherapy is assumed. In Checkmate-032 ([R19-1713](#)) which is an open label phase I/II trial of Nivolumab in patients with SCLC who experienced disease progression after platinum-based chemotherapy, the ORR was 12% [95% CI, 6.5-19.5] (N=109). In KEYNOTE-158 ([R19-1713](#)), which is a phase II basket study of Pembrolizumab, patients with advanced SCLC had an ORR of 18.7% [95% CI, 11.8-27.4] (N=107). In KEYNOTE-028 ([R19-1713](#)), which is a phase Ib basket trial, patients with extensive-stage SCLC showed an ORR of 33% [95% CI, 16-55] (N=24). Based on above result, the futility boundary for cohort C is set as 20% at planned interim futility analysis timing.

For cohort D (GBM), around 20% ORR with Bevacizumab is assumed. In a recent phase II study ([R22-0513](#)) comparing standard dose bevacizumab versus low dose bevacizumab plus lomustine, in patients with recurrent glioblastoma following standard radiation and temozolomide, the ORR was 19% [95% CI, 8-36] (N = 36) based on RANO criteria for the standard dose bevacizumab arm. Based on above results, the futility boundary for cohort D is set as 20% at planned interim futility analysis timing.

For cohort F (2nd line HCC with sorafenib or lenvatinib failure with treatment start date before 15-Jul-2021 (stage I)), around 15% ORR with anti-PD-1 antibody monotherapy is assumed. In Checkmate-040 ([R17-3829](#)) which is an open label phase I/II trial of Nivolumab in patients with advanced hepatocellular carcinoma, the ORR was 20% [95% CI, 15-26] (N=50) in dose expansion phase and 15% [95% CI, 6-28] (N=10) in the dose escalation phase. In KEYNOTE-224 ([R19-0168](#)) which is a phase 2 study of Pembrolizumab in patients with advanced hepatocellular carcinoma previously treated with sorafenib, the ORR was 17% [95% CI, 11-26] (N=104). Based on above result, the futility boundary for cohort F is set as 15% at planned interim futility analysis timing.

Note: Stage II patients (treatment start date after 15-Jul-2021 according to protocol version 7) were not considered in the above sample size justification. Please refer to [Section 7.7.3](#) below for the sample size justification of the stage II patients.

For cohort G (1st line HCC), around 20% ORR with target monotherapies is assumed. In REFLECT ([R20-3051](#)), which is a Phase 3 study comparing Lenvatinib vs. Sorafenib, the ORR was 19% [95%, CI 17-21] (N = 478) for Lenvatinib and 7% [95%, CI 6-8] (N = 476) for Sorafenib. In IMbrave150 ([R22-0533](#)), which is a Phase III trial comparing Atezolizumab plus Bevacizumab vs. Sorafenib, the ORR for Sorafenib arm observed was 12% [95% CI, 7-17] (N = 165). In Checkmate-459 ([R22-0532](#)), which is a phase III study comparing Nivolumab vs. Sorafenib, the observed ORR was 7% [95% CI, 4-10] (N = 372). Based on above result, the futility boundary for cohort G is set as 20% at planned interim futility analysis timing.

Proposed sample size will provide accumulative safety and tolerability data for the investigational combination across different tumor types. Different homogeneous scenarios and heterogeneous scenarios as well as different sample sizes are considered in the simulations to assess the operating characteristics of the BHM approach. The simulation results as shown in [Table 7.7.2: 2](#) below show that, with the proposed cohort size and interim futility analysis in SCLC, MLN, GBM and HCC cohorts, the BHM approach has reasonable probability of reaching the pre-specified response rate under a wide range of scenarios. The probability of observing a $\geq 15\%$ increase in the shrinkage estimator of the ORR under negative scenario is well controlled on cohort level (< 1%). Desirable true positive probabilities ($\sim 60\%$) and false negative probabilities (<2%) are also demonstrated under nugget scenarios for each cohort on proposed sample size.

Table 7.7.2: 1 Early stopping probabilities at interim for cohorts C-H based on observed ORR under different scenarios

Scenario ORR (%) in cohort (C,D,E,F,G,H)	Early stopping criterion Observed ORR	Early stopping probability In cohort C/D/E/F/G/H
Positive: (40,40,25,35,40,25)		3%/3%/8%/6%/3%/8%
Negative: (20,20,5,15,20,5)	Cohort C: <20% (<3 out of 15) Cohort D: <20% (<3 out of 15)	40%/40%/83%/60%/40%/83%
Intermediate: (30,30,15,25,30,15)	Cohort E: <7% (<2 out of 15) Cohort F: <15% (<3 out of 15)	13%/13%/32%/24%/13%/32%
Nugget 1: (20,20,5,15,20,5)	Cohort G: <20% (<3 out of 15)	40%/40%/83%/60%/40%/83%
Nugget 2: (20,20,25,15,20,5)	Cohort H: <7% (<2 out of 15)	40%/40%/8%/60%/40%/83%
Nugget 3: (40,40,25,35,40,25)		3%/3%/8%/6%/3%/8%

Table 7.7.2: 2

Operating characteristics of the Bayesian Hierarchical Modelling approach for final analysis under different scenarios with futility evaluation at the interim

Sample size	Scenario (ORR (%) in each patient cohort)	Probability of shrinkage estimator of the ORR \geq (20%,20%, 35%,35%, 20%,30%, 35%,20%) in at least one cohort at final	Probability of shrinkage estimator of the ORR \geq (20%,20%, 35%,35%, 20%,30%, 35%,20%) in each cohort at final	Probability of shrinkage estimator of the ORR \geq (25%,25%, 40%,40%, 25%,35%, 40%,25%) in at least one cohort at final	Probability of shrinkage estimator of the ORR \geq (25%,25%, 40%,40%, 25%,35%, 40%,25%) in each cohort at final
(40,40, 30,30, 30,30, 30,30)	Positive: (25,25,40,40,25,35,40,25)	99%	91%/91%/82%/82%/ 86%/82%/81%/85%	84%	49%/47%/47%/46%/ 46%/47%/46%/46%
	Negative: (5,5,20,20,5,15,20,5)	1.2%	0.0%/0.0%/0.2%/0.4%/ 0.0%/0.0%/0.6%/0.0%	0.3%	0.0%/0.0%/0.0%/0.1%/ 0.0%/0.0%/0.2%/0.0%
	Intermediate: (15,15,30,30,15,25,30,15)	30%	10%/8%/5%/6%/ 9%/6%/8%/7%	8%	1%/0.9%/1%/1%/ 0.8%/0.7%/2%/1%
	Nugget 1: (25,25,20,20,5,15,20,5)	77%	56%/58%/1%/0.7%/ 0.0%/0.6%/0.8/0.0%	49%	32%/28%/0.4%/0.1%/ 0.0%/0.1%/0.0%/0.0%
	Nugget 2: (25,25,20,20,25,15,20,5)	89%	63%/61%/1%/1%/ 58%/0.5%/1%/0.0%	65%	35%/34%/0.2%/0.3%/ 31%/0.0%/0.1%/0.0%
	Nugget 3: (5,5,40,40,25,35,40,25)	96%	0.0%/0.2%/59%/59%/ 61%/62%/60%/61%	80%	0.0%/0.0%/32%/32%/ 31%/32%/33%/31%
(30,30, 25,25, 25,25, 25,25)	Positive: (25,25,40,40,25,35,40,25)	99%	89%/89%/79%/79%/ 88%/81%/77%/87%	81%	49%/47%/46%/45%/ 47%/46%/46%/46%
	Negative: (5,5,20,20,5,15,20,5)	2%	0.0%/0.0%/0.5%/0.7%/ 0.0%/0.0%/1%/0.0%	0.3%	0.0%/0.0%/0.1%/0.1%/ 0.0%/0.0%/0.1%/0.0%
	Intermediate: (15,15,30,30,15,25,30,15)	34%	12%/9%/6%/7%/ 10%/7%/9%/9%	10%	2%/1%/1%/2%/ 1%/0.8%/2%/2%
	Nugget 1: (25,25,20,20,5,15,20,5)	69%	50%/50%/2%/1%/ 0.0%/0.9%/0.9%/0.0%	45%	29%/27%/0.3%/0.3%/ 0.0%/0.1%/0.1%/0.0%
	Nugget 2: (25,25,20,20,25,15,20,5)	84%	57%/55%/1%/1%/ 53%/1%/1%/0.0%	63%	32%/30%/0.3%/0.3%/ 29%/0.0%/0.4%/0.0%
	Nugget 3: (5,5,40,40,25,35,40,25)	93%	1%/1%/54%/54%/ 61%/59%/56%/62%	75%	0.0%/0.0%/31%/31%/ 30%/30%/31%/30%

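### Section 7.7.2 states false negative probabilities below 2% under the nugget scenarios, but its own table implies 37–44% at the lower bar

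*Protocol*

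**What the plan says.** Section 7.7.2 of the protocol sets out the Part 2 sample size and summarises the simulated operating characteristics of the Bayesian hierarchical model. It makes two statements about error rates.

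- For the scenario in which no cohort is active, the chance that the shrinkage estimate shows a rise of at least 15 points "under negative scenario is well controlled on cohort level (< 1"%).
- For the nugget scenarios, in which only some cohorts are active, it reports true positive probabilities of about 60% and adds that "false negative probabilities (<2%) are also demonstrated under nugget scenarios for each cohort on proposed sample size".

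The supporting numbers are in Table 7.7.2: 2. One column gives, cohort by cohort, the probability that the shrinkage estimate reaches the lower bar, "20%,20%, 35%,35%, 20%,30%, 35%,20%) in each cohort at final". Another does so for the higher bar, "25%,25%, 40%,40%, 25%,35%, 40%,25%) in each cohort at final". The proposed sizes for cohorts A to H are "40,40, 30,30, 30,30, 30,30".

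**The concern.** A false negative is an active cohort that fails to reach the bar. For one cohort and one rule, the true positive and false negative probabilities add to 100%. About 60% for one therefore means about 40% for the other, and a figure below 2% is out by a factor of roughly 20, in the favourable direction.

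The sentence is part of the justification of the cohort sizes. Someone who takes the second figure at face value would think that an active cohort is almost never missed when activity is confined to some tumour types. Part 2 is analysed through the same shrinkage estimate (Section 7.3.1.2), so the true miss rate matters to anyone who reads a low estimate in a single cohort.

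**Working it through.** **Inputs** (all from Table 7.7.2: 2, proposed sample size).

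- Background rates: "Negative: (5,5,20,20,5,15,20,5").
- Lower bar = background + 15 points: 5+15 = 20, 20+15 = 35, 15+15 = 30. This reproduces the stated bars of 20/20/35/35/20/30/35/20%.
- Active rate = background + 20 points, for example 25% in cohort A. The lower bar is thus 5 points below the true rate of an active cohort.
- Nugget 1 has cohorts A and B active: "Nugget 1: (25,25,20,20,5,15,20,5"). Its pass probabilities at the lower bar, cohorts A to H, are "56%/58%/1%/0.7%/ 0.0%/0.6%/0.8/0.0"%, where I read the cohort G entry of 0.8 as 0.8%.

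**Step 1: the plan's figures that do reproduce.** Under the negative scenario the cohort entries are 0.0, 0.0, 0.2, 0.4, 0.0, 0.0, 0.6 and 0.0%. The maximum is 0.6%, so the claim of below 1% holds. The claim of about 60% true positives also holds (step 2).

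**Step 2: nugget scenarios, lower bar.** False negative = 100% − pass probability of an active cohort. False positive = pass probability of a cohort at background rate.

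| Scenario | Active cohorts: pass | False negative | Inactive cohorts: pass (false positive) |
|---|---|---|---|
| Nugget 1 | A 56%, B 58% | 44%, 42% | 0.0–1% |
| Nugget 2 | A 63%, B 61%, E 58% | 37%, 39%, 42% | 0.0–1% |
| Nugget 3 | C 59%, D 59%, E 61%, F 62%, G 60%, H 61% | 41%, 41%, 39%, 38%, 40%, 39% | 0.0–0.2% |

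Overall: true positive 56–63%, false negative 37–44%, false positive at most 1%.

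**Step 3: could another reading of false negative give less than 2%?**

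- No cohort at all reaching the lower bar: 100 − 77 = 23%, 100 − 89 = 11%, 100 − 96 = 4% for nuggets 1 to 3. The sentence also speaks of each cohort.
- Interim stopping of an active cohort: with X ~ Binomial(15, p), P(X<3 | 0.40) = 2.7%, P(X<2 | 0.25) = 8.0% and P(X<3 | 0.35) = 6.2%. These match the 3%, 8% and 6% in Table 7.7.2: 1.
- The smaller sample size in the same table: active cohorts pass with 50–62%, so 38–50% are missed.
- The higher bar: active cohorts pass with 28–35%, so 65–72% fall below it.

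None is below 2%.

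**Step 4: supporting simulation.** I simulated the Section 7.1.2 model (stated priors, futility look at 15 patients, posterior mean, 1,500 trials per scenario). The target rates in the model are not listed, so I ran two assumptions. With targets at the positive-scenario rates, active cohorts in the nugget scenarios pass with 50.6–65.3% (35–49% missed) and inactive ones with at most 1.4%. With targets at background rates, active cohorts pass with 41.1–78.6% (21–59% missed) and inactive ones with at most 2.5%. The published cells are matched only to within several points under the first assumption and less closely under the second, so the finding rests on the table. Neither assumption brings the miss rate near 2%.

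**The case against.** The best defence is that little turns on the sentence. The correct sensitivity of about 60% stands in the same sentence and the full table follows. No hypothesis is tested (Section 7.2), no boundary or decision rule uses the figure, and recruitment ended in December 2021. All of that stands. It limits the consequence, but the stated probability is still wrong.

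The defence is also right about several stronger conclusions that a reader might draw:

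- *That the design misses about 4 in 10 active cohorts in general.* This holds only under the nugget scenarios. In the positive scenario the entries are 91/91/82/82/86/82/81/85%, so 9–19% are missed at the same bar.
- *That this is the only sensitivity given for Part 2.* Table 7.7.2: 2 covers the positive and intermediate scenarios, and Section 7.7.3 gives pass probabilities for cohort F stage II, for example 96% at a true rate of 40%.
- *That 65–72% of active cohorts are missed at the higher bar.* That bar equals the true rate, so even a nearly unbiased estimate would fall short about half the time; the positive scenario shows only 46–49% reaching it. It is not a fair measure of misses, and the figure of about 60% belongs to the lower bar.
- *That the error bore on the decision to stop.* Section 1.3 attributes that decision to comparison with current standards of care and published results, and in second-line HCC to a population no longer representative. It cites neither these bars nor a miss rate.

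**Conclusion.** The sentence is wrong as written. Under the nugget scenarios, at the proposed sample size and the lower bar, the false negative probability is 37–44%, not below 2%. This follows from the protocol's table by subtraction and needs no modelling assumption; the table cells are rounded to about one point.

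That the figure below 2% is a mislabelled false positive probability is an inference. It fits well: every inactive-cohort entry in these rows is 1% or less, it parallels the preceding claim for the negative scenario, and no false negative reading comes close. The contradiction does not depend on it.

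The error lies in how an operating characteristic is described. It does not touch the simulations, the cohort sizes or the planned analysis, and the documents give no ground for linking it to the termination of the trial.

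**What to change.** Replace the sentence in Section 7.7.2 with wording such as: *true positive probabilities of 56–63% (false negative 37–44%) and false positive probabilities of about 1% or less (<2%) are shown under the nugget scenarios at the proposed sample size for the first threshold.*

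Every number is already in Table 7.7.2: 2 or is its complement, so no new simulation is needed. The cost is one sentence and a less favourable stated property.
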